This randomized controlled trial will be conducted in real-world mental health settings providing services to clients within the Massachusetts Department of Mental Health (DMH) community-based system of care, the Mental Health Center of Greater Manchester (MHCGM) in Manchester, NH, the Greater Nashua Mental Health Center of Community Council (GNMHCCC) in Nashua, New Hampshire, and the Community Mental Health Affiliates (CMHA) in New Britain, CT. A total of 144 young adults with SMI and overweight/obesity (BMI ≥ 25) will be recruited from the MHCGM, GNMHCCC, and CMHA, as well as from sites within DMH to participate in a randomized controlled trial. The study will be referred to as the “Fit Forward Lifestyle Trial for in Young Adults.” Participants will be randomized 1:1 to PeerFIT or to Basic Education in fitness and nutrition supported by a wearable Activity Tracking device (BEAT), resulting in approximately 72 clients randomized to PeerFIT and 72 clients randomized to BEAT. Recruitment will occur on a rolling basis with the PeerFIT group intervention starting once at least 2 new people have been randomized to PeerFIT. Thus, we will run open PeerFIT groups in which up to 18 new members are welcome to join at any time during the life of the group. The BEAT individual intervention will begin as soon as 2 participants are randomized to that intervention. This rolling recruitment process combined with open PeerFIT groups is an adaptation to the study design intended to reduce the participant burden of waiting to start the intervention until a full cohort of participants is recruited, which typically takes many months.

INTERVENTION AND CONTROL CONDITION

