PeerFIT Intervention: The 12-month PeerFIT intervention consists of a 6-month intensive phase including: (a) once weekly 90-minute group weight management and exercise session led by a lifestyle coach; (b) once weekly one-hour physical activity session delivered in community settings; and (c) Facebook and mHealth technology (i.e., Fitbits, text messaging support) to increase motivation and facilitate self-monitoring and peer social support for health behavior change. Participants then transition to a 6-month lower intensity phase in which the 90-minute weight management sessions are discontinued. During the low intensity phase, participants will have continued access to the physical activity sessions, social media, and mHealth support described below. A total of 10-18 participants will be enrolled in each of the in-person groups with participants from all groups invited to join the secret PeerFIT Facebook group. The groups will be conducted as open groups with a minimum of 2 and maximum of 18 participants at any given time to offer more diversity and perspective from peer members. After 2 participants are enrolled, each new participant who joins the group will receive an orientation called the “Start Up Session” prior to the group session. The orientation session will be done individually or in a small group setting. The orientation session will last about one hour and will be conducted within one week prior to joining an existing PeerFIT group when possible.

Weight Management and Exercise Sessions. The PeerFIT weight management and physical activity component is adapted from the evidence-based Diabetes Prevention Program designed for individuals at risk for diabetes and cardiovascular disease in the general population. PeerFIT goals are to achieve 5% weight reduction and to increase physical activity gradually to 150 minutes per week over a 6-month period. A private and confidential weigh-in is conducted at the beginning of each session to track participants’ progress. Participants are taught to achieve their weight loss and fitness goals by lowering calorie intake by reducing their consumption of sugar-sweetened beverages and junk foods that are high in sugar and fat and eating fewer processed foods, while adding more fruits and vegetables and lean protein into their diets, and by

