participating in moderate-intensity physical activities. Daily self-weighing and physical activity trackers are used as self-monitoring strategies to promote and reinforce desired behavioral changes. Each 90-minute session includes up to 30-minutes of light to moderate physical activity (e.g., brisk walking) and weight management education and experiential learning activities taught at a beginner level. The PeerFIT lifestyle coach will be trained to deliver basic exercise instruction in a group format for overweight and obese young adults (e.g., walking groups). A certified fitness trainer will be hired as a consultant to the program 1-2 hours per month to develop a structured protocol for conducting the physical activity sessions and provide ongoing supervision for the lifestyle coach. The lifestyle coach will also be trained to lead team building activities, games, and problem solving exercises.

Physical Activity Sessions. In addition, we will offer a one-hour physical activity session each week delivered in community settings over the 12-month study. Due to the current COVID19 social and physical distancing guidelines, the weekly exercise sessions will be moved from community settings to an online format using Zoom technology during the social and physical distancing period. Participants currently enrolled in the study and randomized to the PeerFIT intervention will be notified of this change in the format of the intervention. At the beginning of each week, the PeerFIT coach will call each participant individually to invite them to join the group exercise session. If the participant expresses interest in joining the group the PeerFIT coach will send them Zoom meeting information via text message. This group will follow the same format each week consisting of a warm up, physical activity and cool down lasting no longer than 60 minutes. The group leader and program participants will decide together which activities to pursue each week (e.g., team sports, walking/jogging group, dancing, scavenger hunt). In the event the social and physical distancing restrictions are lifted at the agency prior to the end of this study, the PeerFIT coach may decide to resume conducting the exercise sessions in person.

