Supportive Text Messages. The text messaging component of the PeerFIT intervention is intended to increase participants' self-efficacy for health behavior change according to principles of Social Cognitive Theory. Participants receive encouraging messages and reminders about opportunities to meet the program healthy eating and exercise objectives. The PeerFIT lifestyle coaches send participants text messages 3-5 times per week over the 12-month intervention period. Text messages contain content to promote attendance, and to increase motivation for small goal changes related to healthy eating and being physically active (see Figure 1B). The text messages are structured the same way for each participant, with only minor customizations according to name, gender, and other personal characteristics. This approach is well suited for reaching young adults and promoting engagement in the PeerFIT intervention because text messaging is a ubiquitous form of communication in this age group. In our pilot work text messaging emerged as highly acceptable and useful for easily and quickly conveying practical information such as session times or scheduling, and providing encouragement and helpful reminders. Participants have expressed high satisfaction, ease of use, and appreciation with receiving supportive text messages and reminders.

Fidelity Measurement: Brief and parsimonious fidelity assessments will focus on the extent to which the delivery of the intervention adheres to the program model. Once per month, the lifestyle coaches will be asked to complete a web-based fidelity checklist that covers core components of the intervention. Specifically, the checklists will assess: (1) content covered; (2) activities conducted and time spent conducting the experiential activities; (3) methods for delivering the intervention; and (4) participant attendance at sessions. The research team will collect fidelity data to be analyzed as a potential covariate in the study, while program supervisors hired at the local level will provide continuous feedback to the lifestyle coaches for quality improvement purposes. This approach to turning over quality improvement efforts to agency staff is designed to be practical and feasible in real world settings.

Hey Jim, reminder we have exercise class today, hope you can make it!

Thanks! I'll be there

Great 

Have a good weekend Jim! The weather will be nice so keep finding ways to be active! You are doing awesome! 

Ty, you too!

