3.6.5 Analyses for Study Aims and Hypotheses

Specific Aim 1 (Effectiveness): Mixed effects models will be fit to longitudinal weight, BMI, and cardiorespiratory fitness data. Models will include fixed effects for treatment arm, time and an interaction between treatment arm and time. Additionally, random individual-level intercept and slope terms will be included to account for individual variation in trajectory and simultaneously account for repeated observations within individual. A significant treatment effect of PeerFIT would be indicated by a significant time by treatment interaction accompanied by a mean reduction in weight or BMI or increase in fitness in the PeerFIT group that exceeds the reduction or improvement in the BEAT group (H1a). Similar, non-linear mixed effects models (i.e., longitudinal logistic models) will be fit to the binary cardiovascular risk reduction outcome data (H1b).

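### Aim 1 models and power make no allowance for correlated change within PeerFIT groups; with open groups the effect looks modest, but no planned analysis would show it

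*Combined protocol and SAP*

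**What the plan says.** The PeerFIT Intervention section describes weekly coach-led sessions: "A total of 10-18 participants will be enrolled in each of the in-person groups". It adds that "The groups will be conducted as open groups with a minimum of 2 and maximum of 18 participants at any given time". BEAT is different. The Design Summary says "The BEAT individual intervention will begin as soon as 2 participants are randomized to that intervention", and the Comparison Condition section describes monthly one-to-one sessions with a lifestyle coach.

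Section 3.6.5 gives the Aim 1 models fixed effects for arm, time and their interaction, and states that "random individual-level intercept and slope terms will be included to account for individual variation in trajectory and simultaneously account for repeated observations within individual". H1b uses similar longitudinal logistic models. There is no term for group, coach or site. The Power Analysis for Aim 1 allows for within-person correlation and attrition only. The only sensitivity analyses planned, under Handling of Missing Data, concern missing-data assumptions.

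Two other statements bear on the point. Under Fidelity Measurement, "The research team will collect fidelity data to be analyzed as a potential covariate in the study"; a covariate of that kind does not model correlation between members of one group. Section 9b refers to stratified randomisation, but section 3.6.5 includes no strata.

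**The concern.** When one arm is treated in groups and the other individually, members of a group may change together. A model with participant-level random effects only then understates the standard error of the arm-by-time contrast.

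The protocol gives reasons to think such correlation is possible. For the physical activity sessions, "The group leader and program participants will decide together which activities to pursue each week". Coach fidelity is thought variable enough to measure, and the Aim 2 measures section cites earlier use of the Social Provisions Scale to relate group dynamics to weight loss.

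Only correlation beyond a site effect shared by both arms matters, because a shared effect cancels in the arm comparison. If such correlation exists, the 5% test rejects somewhat too often and the stated power is somewhat favourable.

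**Working it through.** **Inputs.** From the Power Analysis for Aim 1: 72 per arm, two-sided 5%, 80% power, within-person correlation ρ of 0.1-0.7, response 20% against 40%, two visits with correlation 0.5. From the PeerFIT section: 10-18 per group, open membership. From section 5: recruitment from month 6 to month 33, so 27 months. Assumed, because the text gives no figure: ICC 0.01-0.10, and four sites with 18 PeerFIT participants each.

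**1. Reproduce the stated figures.** Detectable slope difference per month = (1.96 + 0.842) × √[2(1 − ρ)/(72 × 72)]. The second 72 is the sum of squared time deviations, 36 + 0 + 36.
- ρ = 0.7: 0.0301. ρ = 0.1: 0.0522. Stated: 0.030-0.052.
- With 57.5 per arm: 0.0337-0.0584. Stated: 0.034-0.059 (57 per arm gives 0.0587 at the top).

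H1b: the two-visit variance factor is (1 + 0.5)/2 = 0.75. Null SE = √(2 × 0.21/72 × 0.75) = 0.0661. Alternative SE = √[(0.16 + 0.24)/72 × 0.75] = 0.0645. Power = Φ[(0.20 − 1.96 × 0.0661)/0.0645] = 86.2% (stated 86%). With 57.5 per arm it is 77.7% (stated 77%). No design effect is needed to obtain any of these.

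**2. Effective cluster size n for open groups.** Let 18 people enter evenly, one every 27/18 = 1.5 months, with pairwise correlation proportional to shared months. The mean row sum of the overlap matrix is 3.72 for 6 months of contact and 6.83 for 12 months. Fixed, fully exchangeable groups would have n = 10 to 18.

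**3. Effect on the planned tests.** Let p be the PeerFIT-specific ICC and s the ICC of a site effect shared by both arms. With arms balanced within site, the ratio of true to assumed variance is f² = (1 − s) + (n − 1)p/2. Then:
- type I error = 2[1 − Φ(1.96/f)]
- H1a power, planned test = Φ(0.842/f)
- H1a power, known-variance test held at a true 5% = Φ(2.802/f − 1.96)
- H1b power, planned test: as in step 1, with 0.24 multiplied by 1 + (n − 1)p in the alternative SE (same ICC assumed on the binary scale)

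Example, n = 6.83, p = 0.05, s = 0: f² = 1 + 5.83 × 0.05/2 = 1.146, f = 1.070, type I error 6.7%.

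| p = 0.05, s = 0 | f | Type I error | H1a planned | H1a at true 5% | H1b planned |
|---|---|---|---|---|---|
| Open, n = 3.72 | 1.033 | 5.8% | 79.2% | 77.4% | 85.3% |
| Open, n = 6.83 | 1.070 | 6.7% | 78.4% | 74.5% | 84.3% |
| Exchangeable, n = 10 | 1.107 | 7.7% | 77.7% | 71.6% | 83.3% |
| Exchangeable, n = 18 | 1.194 | 10.1% | 76.0% | 65.1% | 81.2% |

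**4. Range.**
- Open groups: 5.2-5.3% at ICC 0.01 and 6.6-8.5% at 0.10.
- Half of an ICC of 0.05 shared (p = s = 0.025): 5.1-5.6% for open groups, 6.0-7.2% for exchangeable groups.
- ICC 0 gives f = 1. A fully shared effect gives f² = 1 − s. Neither produces an excess.
- Recruitment also runs "as well as from sites within DMH", so there may be more groups. Six sites of 12 give n = 2.56-4.59 and about 5.5-6.0% at ICC 0.05.
- Simulation (40,000 trials per cell, ICC 0.05, none shared) gave 5.6% and 6.6% for open groups.

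**5. Omitted strata.** If the strata explain 2%, 5% or 10% of slope variance and are left out, f² = 0.98, 0.95 or 0.90 and type I error is 4.8%, 4.4% or 3.9%. Adjusting shrinks the H1a standard error by about 1%, 2.5% or 5%.

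**The case against.** The strongest reply is that little follows in practice. For the documented open format, the planned test loses one to two points of power. The ICC range is assumed, and at 0.01 the type I excess is 0.2-0.3 points. Part of the peer channel is not group-specific, with "participants from all groups invited to join the secret PeerFIT Facebook group". This stands, and it limits the size of the point.

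It is also fair that a group-level analysis cannot settle the question. At ICC 0.05, a group-aware test has about 17 degrees of freedom and 66% power with groups of 10, and about 7 and 53% with groups of 18. The ICC estimate would be zero or negative roughly a third of the time, with a typical 95% interval of about -0.05 to 0.37 (seven groups) or -0.03 to 0.53 (four). This argues against putting a group term in the primary model. It does not argue against a supportive analysis.

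Adding site strata without a group term slightly raises type I error if group correlation exists. In simulation with half of an ICC of 0.05 shared, it moved from 5.0% to 5.3% and from 5.75% to 6.0% for open groups.

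A reader might infer more than the documents support:
- That type I error is 10-15%. This needs fixed exchangeable groups with the larger group sizes and ICCs, not rolling membership.
- That H1b power is really 74-79%. Those values assume exchangeable groups and a different test, held at a true 5%.
- That the stated power could arise only under exact independence. Rounding leaves room for an ICC up to about 0.004 (n = 6.83), and the match also assumes no random-slope variance, although the planned model includes it.
- That H2 implies clustering. The mediation model is specified on individual slopes.
- That the number of groups is missing from the plan. Part of the Study Sites section is not in the available text and may state it.

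**Conclusion.** The point holds in a limited form. The Aim 1 models and power take no account of correlation within PeerFIT groups, and no planned analysis addresses it. Under open groups and an assumed ICC of 0.05, the nominal 5% test runs at roughly 5-7%, depending on how much of the correlation is shared with BEAT through site. A known-variance H1a test held at a true 5% would have 74-77% power.

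This rests on an ICC that the documents do not give, four sites of 18, even entry, overlap-proportional correlation, and no coach clustering in BEAT, although BEAT is also coach-delivered. It is worth correcting before analysis. It does not show that the trial is invalid or seriously underpowered.

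**What to change.** 1. Add the stratification factors actually used, with their interaction with visit, to the H1a model. This gains a little precision and corrects a slightly conservative test. If site is a stratum, pair this with item 2, for the reason given above. For H1b keep strata to main effects: adjustment in a logistic model changes the conditional odds ratio and need not shrink its standard error, and only about 14 BEAT responders are expected (20% of 72).

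2. Prespecify a supportive partially nested sensitivity analysis for H1a and H1b. It should have a PeerFIT-only group effect on change and small-sample degrees of freedom, with BEAT participants as singletons. Define group by a rule that does not depend on attendance, such as the site's group open at randomisation, and fix it before analysis. State in advance which site terms are kept: with one group at each of four sites, site-by-visit effects plus a group term leave about 3 degrees of freedom. Report the estimate and CI, and the ICC with its wide CI. State that a non-significant result alone does not overturn the primary result.

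3. In the Power Analysis for Aim 1, state that H1a and H1b power assumes no within-group correlation, and show both over an ICC range such as 0-0.10.

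The cost is SAP wording, one extra analysis, less favourable power figures and a derived group identifier (Table 1 lists attendance logs but no group variable). Design and sample size do not change. The group-aware test is weak: at ICC 0.05 it needs detectable differences about 18% to 39% larger with groups of 10 to 18, and 81% larger with 3 degrees of freedom.

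Separately, the visit table in section 11 labels BEAT a group intervention. This is a clerical point to reconcile with the Design Summary and the Comparison Condition section.

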3.6.2 Study Variables and Measures

Variables and Measures for Aim 1 (Primary Outcomes)

Primary Hypothesis (H1a). Weight will be measured as the change in body weight over time, and BMI will be calculated by the formula: Weight (kg)/Height(m)². Participants' weight will be measured in pounds (lbs.) on a flat, even surface with the use of a high-quality, calibrated professional digital scale, with the participant wearing indoor clothing and no shoes. Weight will be measured to the nearest 0.1 pound (lb) and duplicate measurements will be made. If the two measurements are more than 0.5 lbs apart, then a third measurement will be collected and the three measurements will be averaged. Scales will be calibrated quarterly by study personnel using standard weights. Weight will be measured in pounds (lbs) for ease of interpretation by participants. Weight will then be converted to kilograms (kg) for calculation of BMI. Participants' height will be measured to the nearest 0.1 cm using a calibrated, mobile stadiometer. The participant stands shoeless on a firm, level surface, with head in the horizontal (Frankfort) plane. Duplicate measurements of height will be collected. If the two measurements are more than 0.1 cm apart, then a third measurement will be collected and the three measurements will be averaged.

Cardiorespiratory fitness will be assessed by the 6-Minute Walk Test (6-MWT), a performance based measure of exercise capacity.⁷ After a baseline pulse has been obtained, participants are asked to walk a measured distance as far as they are able in 6 minutes. Standardized instructions are used to instruct the individual to reach a maximum comfortable pace without running. It is a reliable and valid measure of cardiovascular fitness in diverse populations. We have extensive RCT experience using the 6-MWT in persons with SMI.

Primary Hypothesis (H1b). Clinically significant cardiovascular risk reduction will be assessed by either a ≥5% weight loss or an increase in walking distance of >50 meters on the 6-MWT, both criteria are well-established indicators of clinically significant cardiovascular disease risk reduction.

Secondary Outcomes:

Lipids and A1c: We will test participants' non-fasting cholesterol, triglycerides, and A1c levels via a finger stick blood test done at the baseline assessment. The blood test requires only a tiny sample of blood (40 μ l) and is performed using the Cardio Check and A1c Now Polymer Technology Systems testing devices.

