Power Analysis for Aim 1. Assuming a range of within-person, across time correlations (0.1-0.7), with 144 participants (72 per arm), there will be 80% power, at the two-sided 0.05 significance level, to detect a difference between arms in slope of at least 0.030-0.052 SD units per month, or equivalently, 0.36-0.62 SD units over 12 months. If SDs of weight, BMI, and 6-MWT are similar to those observed previously (approximate weight SD 60, BMI SD 9, and 6-MWT SD 350) with the InSHAPE intervention and active control, these standardized effect sizes are equivalent to difference between arms of 21.6-36.0 lbs, 3.20-5.40 BMI units, and 6-MWT of 126-210m over 12 months. With attrition, power will be slightly lower, or equivalently, detectable differences slightly larger. To provide information on detectable differences if maximum attrition is experienced we also provide detectable differences assuming data from only 115 participants (80% of proposed sample size). In this case, the detectable difference increases to 0.034-0.059 SD units per month or 0.41-0.70 over 12 months yielding detectable weight of 24.6-42.0 lbs, BMI of 3.69-6.30, and 6-MWT of 143-245m over 12 months. True power/detectable difference likely lies in between for 144 vs. 115 participants. In the InSHAPE trial, 38% of participants in the active control arm and 51% of participants in InSHAPE achieved a clinically significant change in cardiovascular risk reduction. Because InSHAPE likely had a strong intervention effect with one-on-one personal fitness training and a gym membership for the active control, we estimate that percentages achieving clinically significant change in cardiovascular risk reduction in this study will be 20% for BEAT and 40% for PeerFIT. Assuming these proportions, there will be 86% power to detect a difference between arms in cardiovascular risk reduction, assuming measures of this outcome at 2 time points and within-person correlation of 0.5. With maximum attrition, the power is reduced to 77%.

Specific Aim 2 (Mechanism of Action): To test the mechanism hypotheses, parallel process latent growth curve models will be fit within a structural equation model (SEM) framework. These models allow for testing mediation of the treatment effect on weight and fitness by changes in self-efficacy (H2a) and peer social support (H2b). It is hypothesized that PeerFIT will have a greater effect on the change over time (slope) of

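### The primary responder analysis (H1b) leaves out the baseline walking distance and weight that help predict response; adding them is a cheap gain in power, not the repair of an error

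*Combined protocol and SAP*

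**What the plan says.** Section 3.6.2 labels H1b a primary hypothesis. A participant responds by losing at least 5% of weight or by "an increase in walking distance of >50 meters on the 6-MWT".

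Under Specific Aim 1 in section 3.6.5, the models for the continuous outcomes have fixed effects for arm, time and their interaction, plus a random intercept and slope for each person. For the responder outcome the text adds: "Similar, non-linear mixed effects models (i.e., longitudinal logistic models) will be fit to the binary cardiovascular risk reduction outcome data (H1b". No baseline covariate is named there. The covariates described elsewhere (demographics, diagnosis, medication, smoking, attendance, device use, fidelity) do not include baseline weight or baseline walking distance.

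On power, the plan expects that response "in this study will be 20% for BEAT and 40% for PeerFIT". With two time points and a within-person correlation of 0.5, "there will be 86% power to detect a difference between arms in cardiovascular risk reduction", falling to 77% at maximum attrition. The continuous outcomes have their own assumption: "Assuming a range of within-person, across time correlations (0.1-0.7), with 144 participants (72 per arm".

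Table 1 schedules weight and the 6-minute walk test (6-MWT) at month 0. The text above that table takes the official baseline weight on day 1 of treatment. Section 4 compares the arms at baseline with chi-square tests and t-tests but ties no adjustment to the result.

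**The concern.** In the continuous models the baseline value enters as the outcome at time 0. In the responder model it cannot, because nobody can be a responder at baseline. All baseline information therefore drops out of a primary comparison.

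That information is useful. Someone who starts with an unusually short walk is likelier to gain more than 50 m whatever the treatment, through regression to the mean; a high starting weight works the same way for weight loss. Left out, this predictable variation counts as noise, and a chance difference between arms in starting values passes into the responder rates. The loss matters most at maximum attrition, where the stated power is already below 80%. If adjustment is not prespecified, adding it after seeing the baseline tests would be a discretionary choice in a primary analysis.

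**Working it through.** **Inputs from the plan.** Allocation: "Participants will be randomized 1:1 to PeerFIT or to Basic Education". Sample size: 72 per arm, or 115 participants in total (57.5 per arm) at maximum attrition. Rates: 20% and 40%. Two visits, responder correlation 0.5. The test level is given for the slope calculation ("there will be 80% power, at the two-sided 0.05 significance level") and is carried over to H1b.

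**1. The stated power.** Effective n per arm = n × 2/(1 + 0.5), so 72 becomes 96 and 57.5 becomes 76.7. With pooled variance under the null,

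z = [√n × 0.20 − 1.96 × √(2 × 0.3 × 0.7)] / √(0.4 × 0.6 + 0.2 × 0.8).

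- n = 96: (1.960 − 1.270)/0.632 = 1.09, power 86.2% (stated 86%).
- n = 76.7: (1.751 − 1.270)/0.632 = 0.76, power 77.7% (stated 77%).

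The plan's figures reproduce as an unadjusted comparison, so they take no credit for baseline covariates.

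**2. How far baseline predicts change.** With equal variances and baseline-to-follow-up correlation ρ, corr(change, baseline) = −√((1 − ρ)/2). This is −0.67 at ρ = 0.1, −0.50 at 0.5 and −0.39 at 0.7.

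**3. Gain from adjustment, by simulation.** Assumptions: two independent, normally distributed components with the same ρ and equal contributions; thresholds set to give 20% and 40% composite response; responder correlation about 0.5. The analysis is a marginal logistic model with arm and time and cluster-robust standard errors, with and without the two baselines, in 2,500 trials per setting. Simulation error in the gains is about 0.5 to 1 point.

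| ρ | 72 per arm: unadjusted → adjusted | Gain | 57 per arm: unadjusted → adjusted | Gain |
|---|---|---|---|---|
| 0.1 | 87.6 → 94.0% | 6.4 | 74.8 → 85.5% | 10.6 |
| 0.3 | 85.8 → 92.2% | 6.4 | 76.6 → 85.4% | 8.8 |
| 0.5 | 85.1 → 88.7% | 3.6 | 75.6 → 80.4% | 4.8 |
| 0.7 | 86.3 → 88.5% | 2.2 | 77.2 → 79.0% | 1.8 |

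(Gains are taken before rounding.)

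- A repeat with 2,000 trials per setting at 144 participants gave 7.5, 5.4, 4.5 and 2.4 points.
- Two other assumed correlations between the 6- and 12-month values gave 2.5 to 8.4 points.
- If one component alone drove response, the gains at 72 per arm would be 10.6, 8.3, 6.0 and 3.6 points.
- Weight at 0.95 with 6-MWT at 0.5 to 0.7: about 1 to 3 points.
- Both at 0.9 to 0.95: about 0 to 1 point.
- Simulated type I error at ρ = 0.1 and 0.7 was 5.6% and 4.4% unadjusted, 6.0% and 4.2% adjusted: close to 5%.

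**4. Chance imbalance.** The standard error (SE) of the difference in baseline means is √(2/72) = 0.167 SD. At a 20% rate, with one component driving response, a baseline difference of d SD moves the responder difference by about 0.280 × √((1 − ρ)/2) × d, where 0.280 is the normal density at 0.842. For d = 0.167 this is 3.1 points at ρ = 0.1, 2.3 at 0.5 and 1.8 at 0.7, against a planned difference of 20. At 1.96 SE it is 3.5 to 6.1 points.

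**5. Why the thresholds were calibrated.** With the plan's 6-MWT SD of 350 and no mean change, P(gain > 50 m) = 1 − Φ(50/(350 × √(2(1 − ρ)))). That is 46% at ρ = 0.1 and 43% at 0.7, already above the 20% expected in BEAT. The plan's SDs, the correlation range and the 20% rate cannot all hold with zero mean change.

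**The case against.** The best defence is that nothing here is broken. Randomisation keeps the unadjusted comparison valid, its type I error is near 5%, and the stated power is right. That stands in full. A reader might infer that the H1b test is biased or its power misstated; the documents support neither. The imbalance point is about error conditional on the baseline actually drawn.

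The size is also open to challenge. The plan gives 0.1 to 0.7 for the continuous slopes only. For H1b it gives 0.5, and that is the correlation between the two responder measures. Using the range between baseline and follow-up is an assumption. Moreover, with the plan's SDs, zero mean change in BEAT and an assumed mean weight of 200 to 260 lb, composite response is 65% to 70% at correlations of 0.1 to 0.7, and comes down to about 21% to 26% only near 0.99, where the gain vanishes. This also stands, though it leans on the SD of 350, so it makes the size uncertain rather than showing it to be nil.

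Two further readings are too strong. One is a gain of at least 5 points at any correlation up to 0.5: at 0.5 the two-component results are 3.6 to 4.5 points with 144 participants. The other is that imbalance could readily move the result by 4 to 7 points: that needs a 0.4 SD difference, which is 0.4/0.167 = 2.4 SE and uncommon.

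Lesser objections stand as limits. A marginal model averaging the arm effect over visits stood in for the planned mixed model with interaction. A pre-randomisation weight is not exactly the value from which percentage loss is computed, whereas the simulation treats them as the same. Section 9b mentions stratified randomisation without naming the factors in the text available, so balance by design on these variables cannot be ruled in or out.

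**Conclusion.** The point holds as lost efficiency in a primary comparison. With two components contributing equally, and baseline-to-follow-up correlations assumed to lie between 0.1 and 0.7, adjustment is worth about 2 to 8 points of power at 144 participants and about 2 to 11 at maximum attrition. Higher correlations shrink it, as shown above, to almost nothing when both measures are very stable. A 1-SE chance imbalance in one baseline moves the responder difference by about 2 to 3 points if that component alone drives response. The evidence settles the direction better than the size. This is a cheap improvement to prespecify.

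**What to change.** In section 3.6.5, state that the H1b logistic model includes baseline 6-MWT distance and a pre-randomisation weight as continuous covariates. Take the weight from screening or the baseline assessment, since the official baseline weight is taken on day 1 of treatment, after the assignment visit in the section 11 visit table. Report the arm effect as a standardised (marginal) risk difference at each visit, which keeps the meaning of the planned 20% against 40%.

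The cost is a sentence or two of text and a standardisation step in the code, with no new data. The one drawback is that an adjusted odds ratio is not comparable with an unadjusted one; the standardised risk difference resolves that.
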